2.1. Study Rationale

This protocol aims to assess the safety and tolerability of phenserine compared to donepezil across various doses administered over a 8-week period in participants with early or mild AD. The study will also evaluate the pharmacodynamic and pharmacokinetic activity of the two drugs to determine dose-response relationships and identify an appropriate dose range for a subsequent Phase 2 study of phenserine.

This study seeks to evaluate the effects of an individualized maximum tolerated dose of phenserine with adequate AChE inhibition to establish an appropriate dose range for future efficacy trials.

The main objective is to test phenserine's disease modifying effect, and therefore we will include a comparator that controls for the known cholinesterase inhibition of phenserine, eg donepezil. This approach allows us to control for the symptomatic effects of cholinesterase inhibition, and to provide direct comparative data on safety and tolerability relative to a well-known AChE inhibitor.

The study duration is relatively short. This is justified by the following rationale: The cholinesterase inhibition effect occurs rapidly within a few hours after intake, and is sustained for about 6 hours. Thus the 4 week duration of the highest dose is sufficient to demonstrate this effect. The time of onset for the effect on cell death markers and other disease mechanisms is expected to start within 4 weeks but definitely within the full 8 weeks study period.

Donepezil, the most used cholinesterase inhibitor in AD with dementia, is included as comparison to control for the cholinesterase inhibition of phenserine, since the main rationale for the PATH1 trial is to explore whether phenserine has an additional disease-modifying effect, including effect on markers of cell-death.

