1.1. Synopsis

Protocol Title:

A phase 1b dose range finding study of Phenserine compared to Donepezil in participants with early or mild Alzheimer's disease.

Brief Title: Phenserine on the Alzheimer's Treatment Horizon, Study 1

Participants will be randomized into two groups: one group will receive phenserine, and the other will receive donepezil. The phenserine group will begin with a dosage of 5 mg twice daily, with the dose being gradually increased every two weeks as tolerated until the maximum dose of 10 mg three times daily is reached. The donepezil group will start at 5 mg once daily, with the possibility of escalation to 10 mg once daily at Week 4, again aiming for a 45% cholinesterase inhibition as tolerated.

The study is designed to last 8 weeks, with a planned total enrollment of 16 individuals from various centers across Norway. Participants will return for follow-up visits every two weeks, during which pharmacodynamic, pharmacokinetic, and safety assessments will be conducted. The final safety follow-up will occur after the completion of dosing for those who complete the study. Early termination visits will include a comprehensive safety follow-up for those who discontinue the study prematurely.

The primary objective of this study is to assess the effects of phenserine compared to donepezil on exosome biomarkers of cell death in individuals with early or mild AD. Additionally, the study aims to evaluate the safety and tolerability profile of phenserine at ascending doses up to 10 mg three times daily (TDS) in comparison to donepezil at doses up to 10 mg once daily (OD). Furthermore, the study aims to analyze steady-state blood levels of phenserine to characterize and compare dose-response relationships for pharmacodynamic outcomes and key safety assessments. Finally, the study will explore changes in specific biomarkers of Alzheimer's Disease (AD) in cerebrospinal fluid (CSF) and blood plasma, as well as assess phenserine's potential short-term effects on cognition using the FLAME Memory Composite and other cognitive sub-tests.

Participants will be enrolled at six centers across Norway. The study will also be supported by the PROTECT platform, which allows for the recruitment of individuals over 50 years of age who have demonstrated cognitive decline, making them suitable candidates for this study.

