1.3. Schedule of Activities (SoA)**Table 1. Schedule of Activities**

	Screening (within 28 days before baseline)	Treatment Period					Safety Follow-up ¹ /EOS (within 28 days after last visit)
		Baseline	W2	W4	W6	W8	
Days \pm Visit window	-28 to 0	0	(14\pm 3)	(28\pm 3)	(42\pm 3)	(56\pm 3)	(56\pm 28)
Informed consent	X						
Demographics	X						
Medical history ²	X						
Concomitant medications	X	X	X	X	X	X	X
Vital signs	X	X	X	X	X	X	X
Physical Exam	X	X	X	X	X	X	X
Neurological Exam	X						X
ECG	X	X	X	X	X	X	X
MMSE	X						
MoCA		X				X	
CDR	X						
MRI ³	X						
Suicidal screening using C-SSRS, modified ⁴	X			X		X	X
Inclusion/Exclusion criteria	X	X					
Randomization		X					
Dispense of IMP ⁵		X	X	X	X		
Adverse events		X	X	X	X	X	
AchE sample collection		X	X	X	X	X	

Dose review (for escalation or de-escalation)			X	X	X		
Exosome Biomarker Collection		X	X	X	X	X	
Blood and CSF-based biomarkers ⁶	X					X ⁷	
PK sample collection			X	X	X	X	
Safety laboratory test ⁸	X		X	X	X	X	X
Urinalysis	X		X	X	X	X	X
FSH test ⁹	X						
Pregnancy test ¹⁰	X		X		X		
FLAME Cognitive battery		X				X	

¹ A safety follow-up visit will be conducted within ~4-weeks after the last study-drug dose for all participants who complete the study or who terminate early.

² Includes prior medication use.

³ Only if no MRI scan available within last 2 years.

⁴ The C-SSRS will only be conducted at the follow-up/EOS visit, if the patient experienced suicidal thoughts after the study treatment period.

⁵ Before any dose escalation. According to tolerability and laboratory tests, the dosage will be reassessed, and participants may need to return to the center for a reduced dose.

⁶ CSF samples will only be collected from patients who specifically consent to CSF sample collection and analysis. If CSF biomarker data are available then there is no need for a new CSF collection at screening

⁷ CSF collection at W8 is voluntary and requires an additional informed consent.

⁸ Renal and liver function will be taken every visit. Full Safety laboratory battery will be taken at screening and safety follow-up.

⁹ Women considered post-menopausal will have an FSH test to confirm their status during the screening period and prior to dosing.

¹⁰ Pregnancy testing is required for all women of childbearing potential within one day prior to receiving the first dose of study drug.

2. Introduction

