To evaluate compliance, the study will measure the extent to which participants take the study medication according to the protocol. Compliance will be assessed using the subject diary and the registration of returned capsules.

Exploratory Objectives:

To evaluate changes in specific biomarkers of Alzheimer's Disease (AD) in cerebrospinal fluid (CSF): A β 1-40, A β 1-42, Tau, and p-tau, and in blood plasma: p-tau217 and NfL.

To assess phenserine's potential short-term effects on specific cognitive tests using the FLAME Memory Composite and other cognitive sub-tests.

To evaluate changes in overall cognitive function using the Montreal Cognitive Assessment (MoCA):

Primary Endpoint:

Changes in exosome biomarkers of pre-programmed cell death, synaptic integrity and function, neuroinflammation, and AD-related protein trafficking in participants treated with phenserine versus those treated with donepezil. Although patients and site staff will be unblinded to the treatment modality administered, they will be blinded to the results of the biomarker evaluations until the study is completed.

Key Secondary Endpoints:

Safety and tolerability of phenserine compared to donepezil in participants with early or mild AD based on the frequencies of reported or observed adverse events (AEs) and serious adverse events (SAE), vital signs, clinical laboratory evaluations, ECGs, and modified CSSRS scores.

Other Secondary Endpoints:

Pharmacokinetic parameters will be assessed at steady state for determination of dose-response relationships for phenserine and donepezil.

Evaluate the proportion of participants in the phenserine arm who achieve the target AChE inhibition of approximately 45%, stratified by dose regime and assess the time required to reach the target AChE inhibition of ~45% and the duration participants maintain this inhibition during the treatment period. Blood samples will be analyzed for Acetylcholinesterase (AChE) activity using a modified Micro-Ellman method (22) normalized to recombinant AChE enzyme activity (refer to Appendix 10).

Compliance will be recorded, based on drug count and subject diary, including the proportion of participants complying with the treatment schedule. Compliance is defined as drug intake within 80-120% of the scheduled dosing.

Exploratory Endpoints:

Assess changes in Alzheimer's Disease (AD) biomarkers in cerebrospinal fluid (CSF): A β 1-40, A β 1-42, Tau, and p-tau, and in blood plasma: p-tau217 and NfL.

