3.1. Table 2. Objectives and endpoints

Objectives	Endpoints
Primary	
To assess the effects of phenserine compared to donepezil on exosome biomarkers of cell death in people with early or mild AD.	Changes in endosomal biomarkers of pre-programmed cell death, synaptic integrity and function, neuroinflammation, and AD-related protein trafficking in participants treated with phenserine versus those treated with donepezil. Although patients and site staff will be unblinded to the treatment modality administered, they will be blinded to the results of the biomarker evaluations until the study is completed.
Secondary	
To evaluate the safety and tolerability profile of phenserine at ascending doses up to 10 mg tds as compared to donepezil at doses up to 10 mg od in participants with early or mild AD.	Safety and tolerability of phenserine compared to donepezil in participants with early or mild AD based on the frequencies of reported or observed adverse events (AEs) and serious adverse events (SAE), vital signs, clinical laboratory evaluations, ECGs, modified CSSRS scores.
Other secondary	
To evaluate steady state blood levels of phenserine and donepezil for the purpose of characterizing and comparing dose-response relationships for pharmacodynamic outcomes and key safety assessments.	Pharmacokinetic parameters will be assessed at steady state for determination of dose-response relationships for phenserine and donepezil
To evaluate the proportion of participants in the phenserine arm who achieve the target cholinesterase inhibition of approximately 45% across different dosing regimens, as well as the time required to reach the target and the duration of maintaining this inhibition.	Proportion of participants in the phenserine arm achieving the target cholinesterase inhibition of ~45%, stratified by dosing regimen and the time to reach the target inhibition and the duration of maintaining this target will be assessed and recorded
To evaluate compliance, the study will measure the extent to which participants	Compliance will be recorded, based on drug count and subject diary, including the proportion of

take the study medication according to the protocol. Compliance will be assessed using the subject diary and the registration of returned capsules.	participants complying with the treatment schedule. Compliance is defined as drug intake within 80-120% of the scheduled dosing.
Exploratory	

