10.3. Statistical Analyses

All primary, secondary and exploratory outcomes will be collected for all participants, except that PK analyses will be performed only for participants randomized to phenserine.

Trial management and data management will be conducted by the University Hospital Stavanger Clinical Trials Unit and the trial statistics will be led by [name], King's College London.

Standard safety data (including all AEs, TEAEs, SAEs, important clinical laboratory findings, and AE-related discontinuations) will be summarized for each treatment arm and dose level.

Exosome biomarker values will be natural log transformed to avoid skewness. To assess the effect of phenserine on a given biomarker, a linear mixed-effects model will be used, with treatment groups (phenserine vs donepezil), time, baseline biomarker, and plate to plate variability in exosome concentration (determined by NanoSight) as fixed effects and participant identification treated as a random effect.

To demonstrate that dropout rates are Missing at Random (MAR), we will calculate the correlation between dropout indicators (e.g., whether a participant drops out) and key covariates, including treatment group, baseline characteristics, and other relevant random effect categories. Based on prior observations (liraglutide trial for example), we expect that the likelihood of dropout will largely be explained by observed factors, especially drug treatment status. A logistic regression model will be used, with the dropout indicator as the dependent variable and treatment status, baseline covariates, and any other relevant factors as independent variables. If the model explains a significant portion of the dropout pattern, this would support the MAR assumption. Sensitivity analyses will also be conducted to assess the robustness of this finding under alternative missingness mechanisms.

For clinical secondary and exploratory outcomes, change from baseline will be calculated at the final study assessment (mean, n, standard deviation, standard error, minimum and maximum scores).

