2.3 Exploratory Objectives

- Changes in CSF and plasma AD biomarkers
- Short-term cognitive effects using FLAME and MoCA

Endpoints are defined exactly as per Protocol Section 3 and Table 2

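### The donepezil arm is there to control for cholinesterase inhibition, but the SAP has no between-arm AChE output, and the protocol contradicts itself on donepezil PK

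*Protocol*

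**What the plan says.** **Purpose of the comparator.** Protocol Section 2.1 says "we will include a comparator that controls for the known cholinesterase inhibition of phenserine", because the main question is whether phenserine has a disease-modifying effect beyond that inhibition.

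**AChE endpoint.** Protocol Section 3, under other secondary endpoints, reads "Evaluate the proportion of participants in the phenserine arm who achieve the target AChE inhibition of approximately 45" per cent. Table 2 reads "Proportion of participants in the phenserine arm achieving the target cholinesterase inhibition of ~45" per cent. SAP Section 2.3 adds "Endpoints are defined exactly as per Protocol Section 3 and Table 2".

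**AChE data.** The Schedule of Activities has a row "AchE sample collection" at baseline and Weeks 2, 4, 6 and 8, with no restriction by arm. Section 9.19 plans to compare the inhibition achieved by the two drugs and to correlate it with clinical outcomes and biomarker changes.

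**AChE analysis in the SAP.** Section 8.3 lists the proportion reaching at least 45%, the time to reach it and the time above it. It names no arm and gives no contrast.

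**PK.** The Table 2 objective is "To evaluate steady state blood levels of phenserine and donepezil for the purpose of characterizing and comparing dose-response relationships". Section 10.3 says "PK analyses will be performed only for participants randomized to phenserine".

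**Target for donepezil.** The synopsis describes donepezil escalation as "again aiming for a 45% cholinesterase inhibition as tolerated".

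**The concern.** Randomising against another cholinesterase inhibitor separates a non-cholinergic effect from a cholinergic one only if the two arms reach similar inhibition, or if the difference is measured and reported beside the result. The escalation text in Protocol Sections 6.1, 6.3 and 6.6 rests on tolerability, so nothing in it brings the arms to a common level of inhibition. If inhibition differs, an exosome difference may partly reflect unequal cholinergic effect, and a true additional effect could equally be masked. The trial is meant to inform a Phase 2 programme, so the risk is that a disease-modifying action is credited or dismissed without the evidence needed to interpret it.

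**Working it through.** **1. The plan's own design figure.** Inputs from Protocol Section 10.3: difference 2.45 SD, two-sided 0.05, 80% power, 4 per arm. For a two-sample t-test, noncentrality = 2.45/√(1/4+1/4) = 3.46 on 6 df, which gives power 0.821. Three per arm gives 0.619. So 4 per arm reproduces. The actual 12:4 split gives power 0.976. Sample size is not in dispute here.

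**2. Tracing the AChE comparison through the documents.**

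| Place | Both arms? | Between-arm contrast? |
|---|---|---|
| Protocol 1.3, Schedule of Activities | Yes, no arm restriction | Not applicable |
| Protocol 3 and Table 2, target endpoint | Phenserine arm named | No |
| Protocol 9.19 | Yes | Yes, but no time point, measure or model |
| SAP 2.3 | Imports Section 3 and Table 2 | No |
| SAP 8.3 | No arm named | No |
| Protocol 10.3 and SAP 7.2, exosome models | Both arms | No AChE term in either |

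Three other SAP items come close but do not fill the gap. Section 5 allows optional summaries of biomarker response by target achievement, labelled post hoc. Section 8.2 plots exposure against inhibition and exposure against exosome markers, but not inhibition against exosome markers. The only correlation specified, in Section 9.1, relates CSF and plasma markers to exosome markers.

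The threshold summaries in SAP 8.3 would not settle comparability even if run in both arms. Mean inhibition could differ widely while few participants in either arm reach 45%.

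**3. How precisely could a between-arm difference be estimated?** Half-width of the 95% CI = t(0.975, 14 df) × √(1/12+1/4) = 2.145 × 0.577 = 1.24 within-arm SD. The documents give no SD for percent inhibition. At assumed SDs of 5, 10 and 15 percentage points, the half-width is 6.2, 12.4 and 18.6 points. For the target proportion, even 4 of 4 donepezil participants at target has an exact 95% CI with lower limit 0.025^(1/4) = 0.398, so 40% to 100%.

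**4. How much could unequal inhibition matter?** Cholinergic share of the exosome difference = (arm difference in inhibition, in SD) × (exosome shift per SD of inhibition). Both inputs are assumptions. With 1 to 2 SD and 0.3 to 0.8, the share runs from 1 × 0.3 = 0.3 SD to 2 × 0.8 = 1.6 SD, against the design difference of 2.45 SD.

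**5. What would adjustment cost?** If the exosome contrast is adjusted for inhibition and the arms differ by D SD, variance inflation = 1 + D²/[(1/12+1/4) × 14] = 1 + D²/4.67. Half-width = t(0.975, 13 df) × √(inflation/3), with residual SD held at 1.

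| D (assumed) | Inflation | 95% CI half-width (SD) | Power at 2.45 SD |
|---|---|---|---|
| 0 | 1.00 | 1.25 | 0.97 |
| 1 | 1.21 | 1.37 | 0.94 |
| 2 | 1.86 | 1.70 | 0.82 |
| 3 | 2.93 | 2.13 | 0.63 |

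Adjustment is least precise where imbalance is largest, which is where it would be wanted most.

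**6. PK passages.** Protocol 2.1, Section 3 (endpoints), Table 2 and 3.2.2 promise PK or dose-response for both drugs. Section 9.18 names only phenserine as analyte, and Section 10.3 limits PK analysis to that arm. SAP 4.4 and 8.2 name no drug, so they do not resolve it.

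**The case against.** A reader might infer that AChE analysis is confined to phenserine and that the donepezil samples have no planned use. The documents do not support that. Section 9.19 plans both a comparison and a correlation, sampling is not restricted by arm, and SAP Sections 2.2, 4.5 and 8.3 name no arm. In Protocol Section 3 the restriction clearly attaches to the proportion; whether it also governs the time and duration measures is arguable. What stands is narrower: the 9.19 plan does not become an SAP output.

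A reader might also infer that an exosome difference can never be attributed to a non-cholinergic effect. That goes too far. The data are collected, the SAP calls itself exploratory and estimation-focused, and its primary objective is a difference between drugs. The attribution language is in the protocol rationale. It is that interpretation which lacks prespecified support.

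It is tempting to put a number on the imbalance by setting the protocol's phenserine peaks against the 45% figure. These are unlike quantities: blood peaks from early volunteer studies, and a CSF optimum tied to cognitive response under donepezil. The actual difference in this trial is unknown.

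Finally, it is fair to say that four donepezil participants cannot establish comparability, and that adjusting for inhibition conditions on a post-randomisation variable that may be a mediator. Both points stand. They argue for a descriptive contrast with its interval and for keeping any adjusted model optional, but not for leaving the contrast out. On PK, the fault is a contradiction, not a consistent restriction to phenserine.

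**Conclusion.** The point holds as a gap between protocol and SAP. Donepezil's stated role depends on comparable cholinesterase inhibition, yet the target endpoint is phenserine-only and the Section 9.19 comparison and correlation reach neither SAP Section 8.3 nor any primary or supportive analysis. Under the assumptions in step 4, unequal inhibition could contribute 0.3 to 1.6 SD to an exosome difference; those inputs are illustrative and the documents supply neither. The missing contrast would be imprecise, at about ±1.24 SD, so it qualifies the interpretation and does not prove similarity.

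The PK conflict is an error as written: the donepezil PK endpoint cannot be delivered under Sections 9.18 and 10.3. The 45% aim for donepezil in the synopsis and the tolerability-based escalation text also need to be made consistent.

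**What to change.** - Define the AChE endpoint in Protocol Section 3 and Table 2 for both arms.
- In SAP 8.3, report percent inhibition from baseline, 100 × (1 − activity at visit / baseline activity), by arm and visit, with the phenserine-minus-donepezil difference and 95% CI. Label it descriptive.
- Show time since last dose beside it. Section 2.1 describes inhibition as sustained for about 6 hours and the donepezil diary specifies bedtime dosing, so samples from one clinic visit may fall at different points of the dosing interval in the two arms.
- Carry the Section 9.19 correlation of inhibition with exosome change into the SAP.
- State that an exosome difference will be described as additional to cholinesterase inhibition only alongside these results.
- An AChE-adjusted exosome model is optional. If run, label it exploratory and say that it conditions on a post-randomisation variable.
- Make Protocol 2.1, 3, Table 2, 3.2.2, 9.18 and 10.3 agree on PK: either remove the donepezil PK endpoint or state that donepezil is assayed.
- Reconcile the synopsis's 45% aim for donepezil with Sections 6.1, 6.3 and 6.6.

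**Cost.** The AChE items need wording, one table or figure and one correlation, from samples already scheduled; SAP Section 1.1 allows amendment before database lock. Time since last dose needs a dose time: the sample phenserine diary has tick boxes for part of day, so the time of the last dose may have to be noted at the visit. PK costs only wording if the donepezil endpoint is dropped, or an added assay if it is kept.

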2.2. Background

In 2018, and in parallel with the conduct of the ELAD study that evaluated liraglutide (an established medication for Type 2 diabetes) for its neuroprotective effects in people with mild to moderate AD, we initiated a new selection process to identify additional drug candidates for repurposing in AD, MCI and other forms of dementia. Drug repurposing, defined as “the application of established drug compounds to new therapeutic indications,” offers a route to drug development that is accessible to academic institutions, government and research council programs, and charities and not-for-profit organizations, complementing the work of pharmaceutical and biotechnology companies. Repurposing an existing drug offers an attractive

way of enhancing traditional drug development and accelerating new treatments for people with AD dementia and MCI into the clinic.

The international expert panel that participated in the 2018 assessment applied the same approach as in the earlier 2012 selection process. A total of five compounds or classes of compounds were nominated for further consideration by the panel. These compounds were ACE inhibitors, antiviral drugs, disease-modifying antirheumatic drugs (DMARDs), fasudil and phenserine. Following several rounds of prioritization, the panel came to a clear consensus that the three highest priority candidates for repurposing in AD, MCI and other dementias were phenserine, fasudil, and antiviral drugs. This protocol is designed to assess the safety and tolerability of phenserine compared to donepezil across a range of doses administered over a 8-week dosing period in participants with early or mild AD. The pharmacodynamic and pharmacokinetic activity of the two drugs will also be evaluated to determine dose-response relationships to identify an appropriate dose range for a subsequent Phase 2 study of phenserine.

Phenserine was initially developed as an acetylcholinesterase inhibitor (AChEI) (3), but there are several mechanisms by which phenserine may act on neuronal and synaptic loss (4), a key common pathway evident in AD. A range of pre-clinical studies indicate that phenserine suppresses interleukin-1b, reduces glutamate-induced excitotoxicity, protects against oxidative toxicity, reduces A-beta levels, improves neural precursor cell viability, elevates neurotrophic brain-derived neurotrophic factor, and inhibits amyloid-beta precursor protein synthesis (4). In the only published phase 2 randomized controlled trial (RCT), phenserine (10-15 mg b.i.d.) conferred improvement in cognition in people with AD receiving 12 weeks of the higher dose of phenserine. Safety and tolerability were very good. The proportion of withdrawals due to adverse events was 6% in the placebo arm and the highest dose groups, indicating that the optimal dose was probably not achieved for most patients. There were also methodological problems, prompting the authors to conclude that the full potential of phenserine for AD has not yet been fully evaluated (3).

The most common side-effects of phenserine are those associated with cholinesterase inhibition, i.e., nausea, vomiting and diarrhoea. The best predictor of cholinesterase linked gastrointestinal effects is the level of cholinesterase inhibition achieved, with the optimal therapeutic threshold being 50% inhibition (5). Given that the completed clinical trials with phenserine did not select patients based on biomarker confirmation of AD (meaning that a considerable proportion of participants likely did not have AD), and that the maximum dose did not lead to side-effects and thus many participants did not likely achieve a sufficiently high dose level, this study aims to evaluate the effects of an individualized maximum tolerated phenserine dose with adequate level of AChE inhibition to determine an appropriate dose range for subsequent efficacy trials.

